3.2.7. Immunogenicity Variables

Baseline values for immunogenicity (antibody) will be the last pre-challenge results available.

For individual participants, fold-rise in antibody titers will be calculated as (post-challenge titer)/(pre-challenge titer), where the pre-challenge value is the result obtained at baseline.

Seroconversion for HAI, NAI, MN, and anti-HA stalk assays will be defined as a minimum 4-fold rise in antibody titer from baseline. This corresponds to either a pre-challenge titer $<$ LOD and a post-challenge titer $\geq 4 \times \text{LOD}$, or a pre-challenge titer \geq LOD and a minimum four-fold rise in post-challenge titer.

4. INVESTIGATIONAL PLAN

4.1. Overall Study Design and Plan

This is an exploratory Phase 1, blinded, randomized, dose-finding influenza virus challenge study in approximately between 62-114 (targeted maximum sample size of 106 active challenge virus plus 8 shams) males and non-pregnant females, 18 to 45 years old, inclusive, who are in good health and meet all eligibility criteria. The clinical study is designed to determine the optimal infectious dose and safety profile of a recombinant influenza A/Texas/71/2017 (H3N2) clade 3C3a strain in healthy adult volunteers.

Potentially eligible study participants may be pre-screened under an active screening protocol (DMID 20-0004) to identify those with HAI antibody titers $\leq 1:40$ specific to the challenge virus strain. During the study screening period of this protocol (Day -45 to Day -3), participants who have not received a seasonal influenza vaccine within the past 4 months and for whom there are no safety concerns from standard safety assessments and screening labs are eligible for enrollment to the study.

Safety assessments and safety labs include a medical history review, physical examination, ECG, a chest X-ray (CXR), HIV and hepatitis B/C testing, baseline SpO₂ saturation, and testing for WBCs, ALC, hemoglobin, platelets, ALT, and creatinine. Women of childbearing potential must have a negative serum pregnancy test at screening and a negative urine pregnancy test on Day -2. Likewise, participants must have a negative drug urine toxicology test (unless the drug is deemed acceptable by the Investigator), negative multiplex respiratory viral test, and a negative SARS-CoV-2 RT-PCR test at screening and on Day -2. After a standard physical exam to exclude active infection or other illness, participants began confinement on Day -2 and remain confined for up to 12 days (Days -2 to 10).

On Day 1, participants are randomized and administered a single challenge dose of either a sham inoculum or a virus dose between 10^4 and 10^6 TCID₅₀. The challenge inoculum is administered using the MAD Nasal Intranasal Mucosal Atomization Device (Teleflex, Morrisville NC) attached to a 1cc syringe. Approximately 500 μ L of study product is delivered in each nostril with the participant in a recumbent position. The dosing plan follows an adaptive dose-escalation schedule (Figure 1) that includes up to 8 different challenge cohorts. This dosing plan was designed to optimize participant safety, starting with a low dose and allowing flexibility to make informed adjustments between challenge cohorts from outcome results of the previous challenge cohort. For the first exposure in humans, the initial low dose challenge is conducted in a group of a targeted total of 13 participants (including 1 sham) to assure the virus is safe with no study-related or unanticipated adverse events observed or reported before further use. Dose escalation to the next (higher) dose and subsequent higher doses, if necessary, is informed by both safety and AR outcomes given a pre-specified decision algorithm for dose-escalating.

Clinical outcomes (see below) and pre-defined halting criteria were used to determine whether the trial moves forward to the higher dose of the challenge strain.

Symptomatic influenza virus infection criteria is based on the virologic assessment and the modified Jackson score. A participant is defined as having symptomatic influenza virus infection if the following criteria are met:

- Viral shedding detected in NP swab(s) by qualitative RT-PCR on at least two days beginning 24 hours after challenge until Study Day 8.
- A cumulative symptom score ≥ 6 from daily component symptoms, including documented fever, computed across any consecutive 5-day window through Day 8 beginning on Day 2 post challenge

using a modified Jackson score. Highest point score per day per sign or symptom will be used. Component signs and symptoms include fever, lymphopenia (< 1000 cells/mL), runny nose, stuffy nose, sneezing, sore throat, headache, cough, malaise, body ache, chills, feverish, shortness of breath, and earache ranked on a 4-point severity scale (0-3). Temperature will be measured three times a day and symptoms will be collected twice daily on the modified Jackson score. A documented fever and feeling feverish will count as one point on the cumulative symptom score.

The study design is presented in [Figure 1](#). The AR is measured as the proportion of participants meeting the criteria for symptomatic influenza infection described above (and in [Section 3.2](#)), and the safety threshold used to halt dose escalation is given by the halting rules described in Section 7.1.1 of the protocol. Note that the AR was determined across all participants in a challenge cohort, blinded to receipt of active challenge virus or sham inoculum.

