# 4. **STUDY DESIGN**

## 4.1 **Overall Design**

This is an exploratory Phase 1, blinded, randomized, dose-finding influenza virus challenge study in approximately between 62-114 (targeted maximum sample size of 106 active plus 8 shams) males and non-pregnant females, 18 to 45 years old, inclusive, who are in good health and meet all eligibility criteria. The clinical study is designed to determine the optimal infectious dose and safety profile of a recombinant influenza A/Texas/71/2017 (H3N2) clade 3C3a strain in healthy adult volunteers.

The study will enroll approximately between 13-39 subjects in each of up to 3 challenge dose groups at 2 sites (Duke University [DU] and University of Maryland [UMD]) for approximately between 62-114 subjects total for the study. We plan to enroll each challenge dose group according to an adaptive dose-escalation schedule (Figure 1) which allows study results (see Section 9.5.6) to be analyzed between challenge cohorts to inform the sample size and virus dose for the next escalation cohort(s). The study timeline anticipates 4-6 weeks of lead-time for studyspecific screening and start-up activities for the initial cohort, and similarly, 4-6 weeks between subsequent cohorts at each site to evaluate study results and turn-over of the clinical unit. However, to compress the overall dosing timelines, challenge cohorts may be performed concurrently or around a 2-week timeline between the sites. We plan up to 2 weeks (Day -2 to Day 8) to complete the clinical in-patient component for each challenge cohort, thus altogether projecting the following to complete the dose-ranging clinical confinement component: up to 3.5 to 4 months, if 3 challenge cohorts evaluated; 4 to 4.5 months, if 4 challenge cohorts evaluated; 5 to 6 months if 5 challenge cohorts evaluated; and 5.5 to 6.5 months if 6 challenge cohorts evaluated. Each participant has an additional 7 weeks of follow-up post confinement. The study period could range from approximately 7.5 months to one year, depending upon the number of challenge cohorts enrolled.

Potentially eligible study subjects may be pre-screened under an active screening protocol (DMID 20-0004) to identify those with HAI antibody titers  $\leq$ 1:40 specific to the challenge virus strain.

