### Safety Threshold

The safety threshold is defined as meeting one of the protocol-defined halting criteria outlined in Section 7.1.1 which includes the occurrence of severe influenza complications in any study subject (Section 2.3.1). If a subject has a severe influenza complication(s), the study staff and subject will be unblinded as to receipt of challenge virus or sham and as to the results of influenza RT-PCR testing for safety evaluation and potential therapeutic intervention with an approved influenza antiviral agent.

In this adaptive schema, the initial cohort (Cohort 1A) for the lowest challenge dose group will include a targeted total of 12 subjects receiving 10^4 TCID50 of the challenge strain and one subject receiving sham placebo. If fewer than 80% of subjects meet the case definition for influenza in Cohort 1A, the dose will escalate to 10^5 TCID50 to include Cohort 2A. If 80% or more subjects in Cohort 1A meet the case definition for influenza, the lowest challenge dose group will be expanded to include a targeted total of 12 additional subjects receiving 10^4 TCID50 of the challenge strain and one subject receiving sham placebo to comprise Cohort 1B. Cumulatively, if fewer than 80% of subjects in Cohorts 1A and 1B meet the case definition for influenza, the dose will escalate to 10^5 TCID50 to include Cohort 2A. If 80% or more of the subjects in Cohorts 1A and 1B meet the case definition for influenza than the lowest challenge dose group will be expanded to include a targeted total of 12 additional subjects receiving 10^4 TCID50 of the challenge strain and one subject receiving sham placebo to comprise Cohort 1C. Cumulatively, if fewer than 80% of subjects in Cohorts 1A, 1B, and 1C meet the case definition for influenza the dose will escalate to 10^5 TCID50 to include Cohort 2A. If 80% or more of the subjects in Cohorts 1A, 1B, and 1C combined meet the case definition for influenza then the optimal dose of 10^4 TCID50 will be selected.

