# Figure 2. Probabilities of further enrollment at the current dose, given varying true infection probabilities, numbers of subjects enrolled at the current dose, and decision thresholds

For illustration, with n=10 subjects enrolled in Cohort 1A at  $10^4$  TCID50, the probability of achieving 8 infections (solid line, top left panel) would be only 0.01 if the true infection probability were 0.4, compared to 0.67 if the true infection probability were 0.8.

Depending on the number of infections observed at each dose level, the final sample size for each dose group will be approximately 10, 15, 20 or 30. Figure 3 shows the estimated infection probabilities and associated exact 95% confidence intervals that would result from observing varying numbers of symptomatic influenza events at a given dose level. The maximum CI width occurs at 50% observed events. With 30 subjects enrolled at the optimal dose, this would correspond to observing 15 symptomatic influenza events and an estimated CI of (31.3%, 68.7%).

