## 9.5.6.2 Interim Review to Determine the Dose for the Subsequent Cohort

After all subjects from each challenge cohort have been discharged from the challenge unit, the infection, symptom, and safety data will be cleaned to prepare for the interim review to determine the dose for the next challenge cohort enrolled.

If the minimum symptomatic influenza AR threshold given in **Figure 1** is met and no halting criteria for safety have been met, the next group of subjects will be enrolled at the same dose level. If the threshold is not met and no halting criteria have been met, the next cohort will be enrolled at the next highest dose level. If the halting criteria are met, the SMC will review to determine whether the study should be halted due to safety concerns.

Data will be considered in aggregate as part of the interim reviews for dose selection, in order to minimize the potential for unblinding.

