4.4.1. Sample Size Considerations

Figure 2 shows the probability of meeting the infection threshold for further enrollment at a dose, given varying numbers of participants enrolled at that dose (10 enrolled in Cohorts 1A or 2A, 15 at Cohort 3A, or 20 in Cohorts 1A+1B or 2A+2B), varying true infection probabilities, and the thresholds for further enrollment. For illustration, with n=10 participants enrolled in Cohort 1A at 10^4 TCID₅₀, the probability of achieving 8 infections would be only 0.01 if the true infection probability were 0.4, compared to 0.38 if the true infection probability were 0.7.

Depending on the number of infections observed at each dose level, the final sample size for each dose group would be approximately 10, 15, 20 or 30. Figure 3 shows the estimated infection probabilities and associated exact 95% confidence intervals that would result from observing varying numbers of symptomatic influenza events at a given dose level. The maximum CI width occurs at 50% observed events. With 30 participants enrolled at the optimal dose, this would correspond to observing 15 symptomatic influenza events and an estimated CI of (31.3%, 68.7%).

Table 2 gives the probability of observing one or more safety events, such as a solicited symptom or an AE of a particular classification in varying total dose group sizes, given underlying true event probabilities.

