5.2. Timing of Analyses

The adaptive study design is based on periodic analysis of symptoms and infection status to determine whether dose escalation criteria have been met. These analyses are blinded, assessing the attack rate across all participants at a given dose level, regardless of receipt of active challenge virus or sham inoculum.

The CSR will be completed when all primary and secondary safety, clinical, and immunological endpoint data are available. Any available data from the exploratory endpoints may also be included. Additional exploratory endpoint data would be included in an addendum to the CSR or standalone analysis report(s) to be incorporated into manuscripts.

A topline report to facilitate timely reporting of primary and secondary objective analysis results will be generated prior to the compilation of the CSR. This will consist of a select portion of tables, which are indicated in [Appendix 1](#) with asterisks alongside titles. These results will be final and will be included in the CSR as well. A portion of these analyses will be presented at the CIVICs network’s 2023 annual meeting, prior to publishing the results in the National Library of Medicine (clinicaltrials.gov).

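### The escalation attack rate counts the sham recipient, but the stated continuation probabilities describe a rule that does not

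*SAP*

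**What the plan says.** **The rule.** Protocol 4.1 (Safety Threshold) sets it for the lowest dose: "If fewer than 80% of subjects meet the case definition for influenza in Cohort 1A, the dose will escalate to" the 10^5 level. Otherwise the dose is repeated, judged cumulatively over Cohorts 1A, 1B and 1C. The 10^5 level works the same way with 70% over 2A, 2B and 2C, and Protocol 4.3 repeats both thresholds. Each of these cohorts is targeted at 12 virus recipients and 1 sham.

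**The denominator.** SAP 4.1 states: "Note that the AR was determined across all participants in a challenge cohort, blinded to receipt of active challenge virus or sham inoculum". SAP 5.2 describes the interim analyses as "assessing the attack rate across all participants at a given dose level, regardless of receipt of active challenge virus or sham inoculum". Protocol 9.5.6.2 is compatible with this: "Data will be considered in aggregate as part of the interim reviews for dose selection, in order to minimize the potential for unblinding".

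**The stated properties.** Protocol 9.3.2 presents Figure 2 as the chance of meeting the threshold for further enrolment, for 10, 15 or 20 subjects. Its example takes 10 subjects in Cohort 1A: "the probability of achieving 8 infections (solid line, top left panel) would be only 0.01 if the true infection probability were 0.4, compared to 0.67" at a true probability of 0.8. SAP 4.4.1 gives the same example: "the probability of achieving 8 infections would be only 0.01 if the true infection probability were 0.4, compared to 0.38" at 0.7.

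**The size range.** Protocol 4.1 plans "for approximately between 62-114 subjects total for the study", and SAP 4.1 repeats the range.

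**The concern.** A sham recipient receives diluent without virus and should not become a case, but still adds one to the denominator under SAP 4.1 and 5.2. The planning sizes do not include that person: 10 and 15 are 12 and 17 less the 2 withdrawals per cohort that Protocol 9.3.2 allows for, and 20 is two cohorts of 10. The worked example shows the conflict. Eight cases in 10 virus recipients is 80% and meets the threshold; with the sham counted it is 8/11 = 72.7%, which calls for escalation.

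At stake is whether the documented operating characteristics belong to the rule that decides escalation. If they do not, readers will overestimate how often a dose near the threshold is repeated, and so how many subjects it will have and how precisely its AR will be known. The lower end of the size range also looks inconsistent with the written algorithm.

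**Working it through.** **Inputs.** Thresholds of 80% and 70% (Protocol 4.1, 4.3); 12 virus + 1 sham per cohort at the two lower doses (Protocol 6.3.1, 9.3.2); planning size 10 (Protocol 9.3.2, SAP 4.4.1); all-participant denominator (SAP 4.1, 5.2). Assumption: no sham recipient meets the case definition. The documents give no rate for shams.

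**Formulas.** Cases needed = threshold × denominator, rounded up. P(continue) = P(X ≥ cases needed), with X binomial on the virus recipients.

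**Step 1: the plan's own figures.** P(X ≥ 8), n = 10, is 0.0123 at p = 0.4, 0.3828 at 0.7 and 0.6778 at 0.8. The stated values are 0.01, 0.38 and 0.67, so they reproduce as 8 of 10 (0.6778 would round to 0.68).

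**Step 2: Cohort 1A with the sham counted.** At 10+1, 0.8 × 11 = 8.8, so 9 cases are needed. At p = 0.8: 10 × 0.8^9 × 0.2 + 0.8^10 = 0.2684 + 0.1074 = 0.3758. At 12+1, 0.8 × 13 = 10.4, so 11 are needed: 12 × 0.8^11 × 0.2 + 0.8^12 = 0.2062 + 0.0687 = 0.2749.

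| Cohort 1A | Cases needed | p = 0.7 | p = 0.8 |
|---|---|---|---|
| 10 virus, sham not counted (as stated) | 8 | 0.383 | 0.678 |
| 10 virus + 1 sham | 9 | 0.149 | 0.376 |
| 9 virus + 1 sham (if n = 10 includes the sham) | 8 | 0.196 | 0.436 |
| 12 virus, sham not counted | 10 | 0.253 | 0.558 |
| 12 virus + 1 sham | 11 | 0.085 | 0.275 |

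**Step 3: smallest passing result among virus recipients, full enrolment.**

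| Look | Sham not counted | Sham counted |
|---|---|---|
| 1A | 10/12 = 83.3% | 11/12 = 91.7% |
| 1A+1B | 20/24 = 83.3% | 21/24 = 87.5% |
| 1A+1B+1C | 29/36 = 80.6% | 32/36 = 88.9% |
| 2A | 9/12 = 75.0% | 10/12 = 83.3% |
| 2A+2B | 17/24 = 70.8% | 19/24 = 79.2% |
| 2A+2B+2C | 26/36 = 72.2% | 28/36 = 77.8% |

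At a first look the two rules part for one result only: exactly 10/12 at the lowest dose (10/13 = 76.9%) or exactly 9/12 at the middle dose (9/13 = 69.2%). At p = 0.8 the 10/12 result has probability 0.558 − 0.275 = 0.283.

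**Step 4: all three looks at the lowest dose, 12 virus recipients per cohort.** The probability of passing is 0.346 without the sham and 0.082 with it at p = 0.8; at p = 0.9 it is 0.849 and 0.544.

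**Step 5: size range.** 1A-1B-1C: 3 × 13 = 39. 1A-2A-2B-2C: 4 × 13 = 52. 1A-2A-3A-3B: 13 + 13 + 18 + 18 = 62. All eight cohorts: 6 × 13 + 2 × 18 = 114. So 62 is one path, not the minimum.

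**The case against.** Several points on the other side stand.

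- The stated probabilities are correct for what they describe, 8 or more infections in 10. A reader might infer a calculation error; there is none. The fault is that they are offered as continuation probabilities beside a different denominator.
- Neither document says that the 10 are virus recipients. That reading follows from 12 less 2. If the 10 includes the sham, 8 of 10 is the all-participant cut-off, but the probability is still 0.436 rather than 0.67, because only 9 people can become cases.
- It is tempting to say that the sham moves the thresholds from 80%/70% to 88-92%/78-83%. Part of that is whole-number rounding. Against the cut-offs without the sham, it adds about 4 to 8 percentage points at full enrolment. Likewise, setting 0.67 against 0.27 changes the cohort size as well as the rule.
- A reader might infer that the final ARs or the dose ranking are biased. The documents do not support this: SAP Table 14 estimates the AR by dose group with sham in its own column, and under Protocol 9.5.2 a dose that was escalated past remains eligible as optimal.
- The plan disclaims predetermined precision and deliberately favours larger groups at higher doses (Protocol 9.2, SAP 4.4). That makes more escalation tolerable, but nothing says that the sham was meant to raise the bar.
- Figure 1, which holds the decision criteria, is not reproduced in the text reviewed and might give case counts. Protocol 9.3.2 also implies a threshold after Cohort 3A that the readable text does not give, so the list of paths may be incomplete.
- One sham case would remove the effect in that cohort, and the SAP provides for infected shams (Tables 25, 40, 43).

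**Conclusion.** The concern holds as a mismatch between the escalation rule and its documented properties. On the SAP's all-participant denominator, the chance of repeating the lowest dose after Cohort 1A is roughly half the stated value or less: 0.38 against 0.67 at a true AR of 0.80, and 0.15 against 0.38 at 0.70, at planning size. The like-for-like figures at 12 per cohort are 0.27 against 0.56 and 0.085 against 0.25. If the planning 10 already includes the sham, the gap is smaller but remains.

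The consequences are for escalation decisions, group sizes and precision. The result rests on no sham recipient becoming a case and on one sham per cohort, which is a target only. The stated minimum of 62 is also wrong on the written algorithm, which allows totals of 39 and 52; this is a separate and smaller point.

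**What to change.** 1. Reconcile Protocol 4.1, 4.3 and 9.3.2 with SAP 4.1, 4.4.1 and 5.2 so that one denominator for the escalation AR is stated throughout. Which one is for the sponsor to decide and justify.
2. Recompute Figure 2 and both worked examples for that denominator, giving the number of cases needed at each look and saying whether n counts the sham.
3. The SAP describes the escalation AR in the past tense, so add a retrospective check. Using the actual number of shams in each cohort, the SDMCC should report in aggregate whether any completed escalation decision would differ on virus recipients only. The planned one per cohort should not simply be subtracted: Protocol 6.3.2 provides extra randomization slots and does not replace late dropouts, so the count may differ from target.
4. Correct the lower end of the size range in Protocol 4.1 and SAP 4.1, or state the condition that rules out the 39- and 52-subject paths.

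The cost is wording, one figure and an aggregate recalculation. It needs no new data, and no individual assignment need be disclosed to blinded staff.

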4.2. Discussion of Study Design, Including the Choice of Control Groups

Participants were randomized to receive either Live Influenza Virus RG-A/Texas/71/2017 (H3N2) challenge virus or sham inoculum within each challenge dose group. Participants received one of three doses of challenge virus depending upon the challenge cohort into which they enrolled using the adaptive trial design. The targeted ratios of participants randomized to receive either challenge virus or sham inoculum are given below.

Challenge Cohort	Challenge Dose Group	Challenge virus: Sham inoculum
1A, 1B, 1C	10^4 TCID ₅₀	Targeted 12:1
2A, 2B, 2C	10^5 TCID ₅₀	Targeted 12:1
3A, 3B	10^6 TCID ₅₀	Targeted 17:1

Sham inoculum was included as a control primarily to maintain the blind of the study, so neither participants nor study staff assessing participants' symptoms could be certain of the study assignment and unintentionally introduce bias in determining the incidence of influenza symptoms.

